#### DATA AND SAFETY MONITORING PLAN

Some participants may find the daily questions of the HR application boring or tedious, or they may be bothered by the phone battery usage required to keep the app running, and may choose to discontinue using the application or withdraw from the study. Participants may become seriously medically ill and decide not to participate. In addition, if new psychiatric symptoms develop or change in severity, or the abuse situation escalates, we may recommend removal from the study and provide referrals for the appropriate treatment needed. All EM victims will continue to receive EM resolution services from DFTA regardless of their participation or termination of participation in the study intervention.

14. Describe the anticipated adverse events and risks of study intervention(s), agent(s) and/or device(s) in detail (e.g., potential risk of the study drug, including potential drug interactions, psychological risks; physical risks). Assess their seriousness and incidence of complications or adverse events when known. Include animal data if trials in humans have not been performed. As all participants will be DFTA clients receiving EM resolution services, we can expect to receive weekly updates from EM staff regarding the participant's depressive symptoms and functioning. Cornell research staff will also assess changes in depressive symptoms at regular intervals. Patient's health and clinical care will always take priority over study participation. Participants may not want to continue completing daily questions via the HR application and will be free to discontinue usage at any time. Participants will also have the option to disable cellular data use for the app through their device settings.

15. Given the risks identified, describe what monitoring is needed to immediately recognize the adverse events that do occur. Study interviewers will be Weill Cornell research staff who are trained in assessments with older adults. They will specifically inquire about depressive symptoms, falls, and hospitalizations. DFTA EM staff are also trained to monitor the Page 18 of 34 5/9/19 1:02 PM participant's mental state (in addition to abusive incidents) and will report any notice of falls, hospitalizations, and increasing symptom severity to Weill Cornell staff and the principal investigator. If any moderate to severe symptom changes (or new symptoms) are noted, we will consider alternative options to maximize the participant's well-being. In addition, we will ask all participants about the burden of active and passive sensing and daily smartphone usage, to identify any potential negative consequences of using the HR app. We do not expect any additional risk of adverse events by adding active and passive sensing data collection.

16. Describe what measures will be taken to minimize any negative impact on subjects resulting from study closure or a subject being terminated from the study. All participants will continue to receive EM resolution services from DFTA if they choose to withdraw from the study. Referrals to external mental health agencies will be offered to participants who drop out of the study in order to address any ongoing depressive symptoms.

17. Describe the adverse event grading based on severity, attribution, and expectedness (including frequency) that will be used, to whom they will be reported and how often. The study will adhere to the adverse event grading guidelines provided by Weill Cornell's Office of Research Integrity and Assurance. All adverse events will be reported to the Weill Cornell IRB in the timeline indicated by the Weill Cornell Human Research Protection Program Immediate Reporting Policy.

18. In addition to the IRB, specify to whom you will be reporting unexpected adverse events to promptly. PLEASE NOTE all reportable AEs should be reported to the WCMC IRB as per WCMC AE reporting policy. We will periodically report adverse events to the DSMB, in addition to reporting to the IRB as per Weill Cornell's policy.

19. Will you be using a medical monitor? No

20. Please justify why no monitor is being used. Medical information will be self-reported by participants during the baseline and follow-up research assessments.

PROTOCOL TITLE: EM/PROTECT: Improving Depression in Elder Mistreatment Victims

PRINCIPAL INVESTIGATOR: [name] [name], PhD, Weill Cornell Medicine

IRB Protocol #: 1703018101

ClinicalTrials.gov Identifier: NCT03241225

Current Version: November 24, 2021

Descriptive statistics for continuous (median and interquartile range; IQR) and categorical (frequency and percentage) were reported on demographics and clinical characteristics of two treatment groups at baseline. A Mann-Whitney test and Fisher's exact test were conducted to test the difference between PROTECT and Usual care for continuous and categorical variables, respectively.

Remission rate was defined as the percentage of participants with MADRS scores  $\leq 10$  at Week 9. Response was defined as a reduction of  $\geq 50\%$  in MADRS scores from baseline to Week 9. We conducted two mixed-effects linear regression models to compare the trajectories of change in MADRS scores and WHOQOL scores between PROTECT and Usual care, respectively. Each model included fixed effects of treatment (PROTECT vs. Usual care), time, and their interaction, as well as a participant-specific random intercept. Both models were adjusted for age and gender. Site and its interaction with treatment were initially included in the model but were dropped as their effects were statistically non-significant. A two-sided p-value less than 0.05 was considered statistically significant. Intent-to-treat analyses are presented with all available data in the mixed-effects models. Remission and response rates were calculated based on 30 patients with complete data. All analyses were conducted in R 3.6.1 (R Foundation for Statistical Computing; <http://www.r-project.org/>).

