often adult children or spouses. Perpetrators are likely to be male, socially isolated, unemployed, have substance abuse, mental or physical health problems, a police record, or financial problems. Mistreatment victims have high rates of depressive symptoms. Victims of EM have one of the highest rates of depression among older adults (<http://www.aoa.acl.gov/>). A population-based study found that mistreatment victims had significantly higher rates of depressive symptoms (31.6% vs. 6.8%) and suicidal ideation (16.4% vs. 3.4%) than non-mistreated older adults. In a 7.6 year follow-up of an urban sample, adults with concurrent mistreatment and depressive symptoms had higher rates of mortality than non-depressed victims of mistreatment. In our own work in NYC, 34% of victims endorsed significant depressive symptoms and 16% reported suicidal ideation. Consistent with our Center's deployment focused model, EM/PROTECT has been developed through an iterative process with the NYC DFTA Elderly Crime Victim Resource Center (ECVRC). EM aims to install protection measures, while PROTECT targets the behavioral Page 23 of 34 5/9/19 1:02 PM consequences of stress on the CCN and the reward networks thus reducing the experience of stress.

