#### INCLUSION AND EXCLUSION CRITERIA

Inclusion Criteria: 1) 55 years of age or older 2) capacity to consent (per EM staff) 3) significant depression (per EM staff) as indicated by a score of 10 or above on the Patient Health Questionnaire-9 (PHQ-9), a widely used screening tool routinely administered in EM agency settings (the PHQ-9 has a sensitivity of 88% and a specificity of 88% for major depression) 4) need for EM services.

Exclusion Criteria: 1) Active suicidal ideation (MADRS item 10 >4) 2) inability to speak English 3) Axis 1 DSM-5 diagnoses other than unipolar depression or generalized anxiety disorder (by SCID) 4) MOCA

score of 23 or less 5) Severe or life-threatening medical illness 6) EM emergency and or referral out of EM agency (per EM staff

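### Remission is MADRS of 10 or less at Week 9 with no baseline condition, and entry sets no minimum MADRS, so a participant can be counted as remitted without improving

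*SAP*

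**What the plan says.** **Entry (Protocol, Inclusion and Exclusion Criteria).** Depression severity is judged by elder mistreatment (EM) agency staff, "as indicated by a score of 10 or above on the Patient Health Questionnaire-9 (PHQ-9"). The MADRS enters eligibility at one point only, as a safety exclusion: "Active suicidal ideation (MADRS item 10 >4"). No minimum MADRS total is set. The diagnostic criterion is also an exclusion: "Axis 1 DSM-5 diagnoses other than unipolar depression or generalized anxiety disorder (by SCID"). It removes other disorders but does not require that a depressive disorder be present.

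**Outcome (SAP, paragraph defining remission and response).** "Remission rate was defined as the percentage of participants with MADRS scores" of 10 or less at Week 9. Nothing is said about the baseline score or about change. The next sentence does use baseline: "Response was defined as a reduction of" at least 50% in MADRS from baseline to Week 9. Both rates are computed on 30 patients with complete data.

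**Role of the outcome.** The protocol's effectiveness objective is a reduction in clinically significant depressive symptoms on the MADRS, together with better quality of life. Both documents analyse MADRS and WHOQOL in linear mixed models. Remission appears only in the SAP, which names no between-arm model for it.

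**The concern.** Entry and remission are set on different scales by different assessors: a PHQ-9 screen by agency staff, and a MADRS scored by trained blinded raters. Passing the first does not guarantee a score above the cut-off on the second. Remission is normally read as a move from a depressed state to a non-depressed one. As defined here, it is a state at Week 9 that some participants may already have been in at baseline.

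At stake is the meaning of the remission rate. The protocol says its focus is effect sizes and clinical relevance, and that the study prepares for a fully powered trial. A remission rate is the kind of figure a later design would take over. If it includes people who were never above the cut-off, it overstates how many participants recovered.

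**Working it through.** The documents state no expected remission rate or sample size for remission, so there is no figure to reproduce. The check is one of logic, followed by illustrations of size.

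**1. Can the case occur under the stated rules?** Take PHQ-9 = 10, baseline MADRS = 9, Week 9 MADRS = 9, with no exclusion met.

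- Entry: PHQ-9 is at least 10 and no MADRS total is required, so the person is eligible.
- Remission: 9 ≤ 10, so the person is a remitter with zero change. A rise from 9 to 10 also counts.
- Response: the fall is 0%, below 50%, so the person is not a responder.

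No other text in either document closes this gap.

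**2. How many of the 30 could be affected?** The baseline MADRS distribution is not given. Assume it is normal among completers, with mean m and SD s. The share at or below 10, with continuity correction, is f = Φ((10.5 − m)/s), and the expected number is 30f.

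| Assumed mean | SD 5: share (of 30) | SD 7: share (of 30) |
|---|---|---|
| 15 | 18.4% (5.5) | 26.0% (7.8) |
| 18 | 6.7% (2.0) | 14.2% (4.3) |
| 20 | 2.9% (0.9) | 8.7% (2.6) |
| 22 | 1.1% (0.3) | 5.0% (1.5) |
| 25 | 0.2% (0.1) | 1.9% (0.6) |

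The range is 0.1 to 7.8, or about 0 to 8 of 30.

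**3. What does each one do to the rate?** Each participant who starts and stays at or below 10 adds 1/30 = 3.3 percentage points to the pooled rate.

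**4. Effect on the level.** Let f now be the share who start and stay low, and r the remission rate among those starting above 10. The reported rate is f + (1 − f)r. With an assumed r = 30%:

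- f = 5%: 0.05 + 0.95 × 0.30 = 33.5%
- f = 10%: 0.10 + 0.90 × 0.30 = 37%
- f = 20%: 0.20 + 0.80 × 0.30 = 44%

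**5. Effect on the contrast.** If f is the same in both arms, the difference is (1 − f)(r₁ − r₂). With assumed rates of 40% and 20%, the difference of 20 points becomes 46% − 28% = 18 points at f = 10%, and 52% − 36% = 16 points at f = 20%. The contrast shrinks and does not favour either arm.

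**The case against.** The strongest reply is that this is only a possibility, in an outcome that does not carry the effectiveness conclusion. Much of that stands. The mixed model uses the MADRS score itself, so a participant who goes from 9 to 9 contributes zero change and is not miscounted. Randomization at participant level balances low starters between arms in expectation. Chance imbalance in a small sample is a risk for every baseline factor.

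Four stronger readings are tempting, but the documents do not support them.

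- **That the remission rate is in fact inflated.** Without baseline MADRS data this cannot be known. The number affected may be zero.
- **That the size follows from the screen's accuracy.** The protocol says that "the PHQ-9 has a sensitivity of 88% and a specificity of 88% for major depression", and that "34% of victims endorsed significant depressive symptoms", so a reader might compute a false-positive share. That share would concern people without major depression, not people with MADRS of 10 or less. It would also pair an accuracy for major depression with a prevalence of depressive symptoms, and ignore the other entry criteria.
- **That one participant shifts an arm's rate by a known amount.** The SAP gives only the total of 30. The protocol mentions a larger number of EM/PROTECT participants, so an equal split cannot be assumed.
- **That response has the same flaw.** It does not, because an unchanged participant is not a responder. Needing fewer points from a low baseline is a property of any percentage definition.

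What remains is that the definition allows remission without improvement, and that the SAP asks nobody to check how often this happened.

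**Conclusion.** The point holds as a gap between the entry criteria and the remission definition. That part rests on the text alone and needs no assumption. The size does: about 0 to 8 of 30 is what the assumed normal baselines give, and the documents favour no value within that range. It is also an upper figure for those counted without improving, since some low starters may rise above 10 or fall further by Week 9. If low starters exist, the remission level is raised in both arms in expectation and the contrast is pulled towards zero, with chance imbalance possible in either direction. The conclusions from the MADRS and WHOQOL mixed models stand as they are. This is an inexpensive improvement to a supporting outcome, not a threat to the main analysis.

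**What to change.** Add two items to the SAP's remission paragraph:

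1. For each arm, the number of the 30 completers with baseline MADRS of 10 or less.
2. The remission rate by arm among completers with baseline MADRS above 10, shown beside the rate as now defined and with its denominator.

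The SAP is written in the past tense, which suggests that the analysis is done. In that case, label the second item post hoc and keep the defined rate in the report, so that the outcome is not silently replaced. A baseline-adjusted logistic model is not advised, because with 30 completers its estimates would be unstable.

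The cost is a few lines of SAP text and a re-count. Baseline MADRS is already a scheduled assessment, so no new data are needed. The downside is a slightly smaller denominator and probably a lower remission rate. If nobody started at 10 or less, one sentence saying so closes the matter.

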## STUDY DESIGN

EM/PROTECT, a behavioral intervention for depressed elder mistreatment (EM) victims, was designed to work in synergy with EM mistreatment resolution services that provide safety planning, support services, and links to legal services. PROTECT is built on a model which postulates that chronic stress promotes dysfunction of the cognitive control (CCN) and reward networks, impairing the victims' ability to flexibly respond to the environment and limits their rewarding activities. PROTECT therapists work with EM victims to develop action plans to reduce stress, and to increase rewarding experiences. EM/PROTECT has been designed in an iterative process with community EM providers of the New York City (NYC) Dept. for Aging (DFTA) to use agencies' routine depression screening and referral for service. We propose to collect data on feasibility and acceptability of EM/PROTECT. We will compare the effectiveness and target engagement of EM/PROTECT with EM enriched with training of EM staff in linking EM victims to mental health services (EM/MH) in order to position us for a fully powered R01. To ensure rigor and reproducibility, EM/PROTECT or EM/MH will be offered to randomly assigned depressed EM victims, and standardized assessments will be conducted by trained raters blind to participant assignment and our hypotheses. The training of staff and therapists will follow high standards of intervention fidelity. EM staff will screen using routine standardized measures and refer depressed victims to study staff who will describe the study and obtain consent and conduct research assessments. We will use brief validated instruments to assess the outcomes, explore the added value of mobile technology measures, and study the effect of sex in each aim. The EM agencies of NYC are overseen and funded by DFTA. We will Page 22 of 34 5/9/19 1:02 PM begin by working with the Elderly Crime Victims Resource Center (ECVRC), as we have successfully partnered with them in the past for our initial exploratory work ([name] et al., 2015a and b). We will then work with DFTA to identify a second site. At both sites we will provide refresher training in depression screening and strategies for linking victims to mental health using the Open Door approach we jointly developed with DFTA. Randomization at the participant level will be conducted by the Methods Core (random numbers in blocks of varying size). Both agencies will conduct depression screening. EM workers will not be blind to treatment arm. We are aware that their knowledge of treatment assignment may influence the EM services they provide. For this reason, we will record and compare their services between the two treatment arms to inform the design of the R01 proposal that will follow this R34 study.

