We plan to recruit 4.5 subjects per month over 14 months to achieve a final sample of 80 subjects. We will recruit 2 licensed clinical social workers to administer the PROTECT therapy sessions with clients. The larger number of EM/PROTECT participants will allow a better view of effectiveness and reach/feasibility/acceptability. Effectiveness objective: In separate linear mixed models, we will analyze primary (MADRS, WHOQOL assessed at baseline, 6, 9 and 12 weeks) and secondary measures of effectiveness (PAM, ratings of mood and anhedonia assessed daily) with a subject-specific random intercept and slope and fixed effects for time, treatment, EM agency, LCSW, treatment x time interaction. We will use model building and fitting strategies. In the final model, we will also estimate end of treatment improvements in outcome (from baseline) within each treatment group. As Page 24 of 34 5/9/19 1:02 PM this is an inadequately powered R34 study, we will control for false discovery rate using the Benjamini-Hochberg approach, and not the Family-Wise Error Rate, to adjust for multiple comparisons of secondary outcomes. The focus of our analysis would be to obtain preliminary signals of effectiveness by estimating effect sizes (95% CI) and assessing clinical relevance. Using approaches of Initiative 2.1 (Methods Core), we will conduct exploratory joint analysis of primary and secondary longitudinal outcomes. We will also test between group differences in smartphone measures using the time series approach of Initiative 2.1 (Methods Core). Reach/feasibility/acceptability objective: We will calculate estimates and 95% CI of the following measures for all subjects and for each sex separately. Reach: Proportions screened and met study criteria in both conditions. Feasibility: Among EM/PROTECT clients, proportions of: treatment drop-outs, assessment completions, smartphone use. Proportion of EM/MH victims who contacted mental health services. Acceptability by clients: We will analyze victim satisfaction (CSQ) recorded at baseline, 6, 9, 12 and 16 weeks as in Aim 4. Benchmark tests of feasibility (75% session attendance rate and 70% smartphone ratings) and acceptability will be performed using one-sample z-test of proportions.

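### The mixed models leave baseline MADRS and WHOQOL unadjusted, which is unbiased but can widen the confidence intervals the study exists to report

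*SAP*

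**What the plan says.** The Protocol (Study Design, effectiveness objective) models the "primary (MADRS, WHOQOL assessed at baseline, 6, 9 and 12 weeks", with a random intercept and slope per participant and "fixed effects for time, treatment, EM agency, LCSW, treatment x time interaction". Baseline is therefore one of four repeated outcomes, the treatment main effect lets the arms differ at baseline, and no baseline covariate is listed. The only end-of-treatment estimate named is within arm: "we will also estimate end of treatment improvements in outcome (from baseline) within each treatment group". The same paragraph describes the study as underpowered and sets the focus as "estimating effect sizes (95% CI) and assessing clinical relevance". Earlier in Study Design: "Randomization at the participant level will be conducted by the Methods Core".

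The SAP fits two models "to compare the trajectories of change in MADRS scores and WHOQOL scores". "Each model included fixed effects of treatment (PROTECT vs. Usual care), time, and their interaction", with a random intercept only. "Both models were adjusted for age and gender". It gives neither the visits modelled nor the coding of time. That baseline is an outcome there is inferred from the reference to change; the text does not state it.

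**The concern.** Randomisation of individuals gives both arms the same true baseline mean. A model with a free treatment main effect still estimates a baseline difference, and the treatment-by-time term then compares changes from baseline. That subtracts the whole of any chance baseline imbalance, when only the part that predicts follow-up should be removed. The estimate stays unbiased, but it is usually noisier than one that uses baseline as a covariate or constrains the baseline means to be equal.

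This matters here because interval estimates are the stated product and are meant to inform a larger trial. The baseline score is already collected, so any precision it offers needs no new data.

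**Working it through.** **Inputs from the documents.** Visits at 0, 6, 9 and 12 weeks and a planned N of 80 (Protocol, Study Design); two-sided 5% level and 30 participants with complete data for remission and response (SAP). There is no stated SD, correlation or CI width to reproduce.

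**Assumptions.** Between-visit correlation ρ; k = baseline SD / follow-up SD, with follow-up SD set to 1. Arms of 40 and 40 for the example. The variance ratios were the same at 53:27 and 15:15.

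**Formula.** With categorical time and complete data, the planned contrast at one visit is a difference in mean change. Per participant:

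- planned (change) variance: 1 + k² − 2ρk
- baseline-adjusted variance: 1 − ρ²
- ratio: (1 − ρ²) / (1 + k² − 2ρk), which is (1 + ρ)/2 when k = 1

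For example, k = 0.8 and ρ = 0.5 gives 0.75 / (1.64 − 0.80) = 0.893.

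**Variance ratio, adjusted / planned.** The dropout rows are for week 12, by generalised least squares with monotone dropout, half of those missing having a baseline score only.

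| Case | ρ=0.4 | 0.5 | 0.6 | 0.7 |
|---|---|---|---|---|
| k=1.0, complete | 0.70 | 0.75 | 0.80 | 0.85 |
| k=0.8, complete | 0.84 | 0.89 | 0.94 | 0.98 |
| k=0.7, complete | 0.90 | 0.95 | 0.98 | 1.00 |
| k=1.0, 20% missing | 0.74 | 0.79 | 0.83 | 0.87 |
| k=1.0, 40% missing | 0.79 | 0.83 | 0.86 | 0.90 |
| k=0.8, 20% missing | 0.87 | 0.91 | 0.95 | 0.98 |

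The CI width ratio is the square root. The first row gives intervals 16%, 13%, 11% and 8% narrower.

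**Cost of estimating the baseline slope.** Multiply by 1 + 1/(N − 4): 1 + 1/76 = 1.013 at N=80 and 1 + 1/26 = 1.038 at N=30. The first row at N=30 becomes 0.73, 0.78, 0.83, 0.88. The least favourable cell (k=0.7, ρ=0.7, N=30) is 1.00 × 1.038, a loss of about 4% in variance.

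**Example.** 40 per arm, ρ=0.5, k=1:

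- planned half-width: 1.96 × √(2 × 0.5 × 2/40) = 0.438 SD
- adjusted half-width: 1.96 × √(0.75 × 2/40 × 1.013) = 0.382 SD

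**Other model forms.**

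- Linear time, ρ 0.3 to 0.7: ratios 0.540–0.817 at k=1 and 0.742–0.989 at k=0.7.
- The Protocol's random intercept and slope (intra-subject correlation 0.5, slope SD over 12 weeks 0.5 or 0.8 of baseline SD): 0.78 or 0.82 at week 9, and 0.80 or 0.85 at week 12.

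**Bias check.** In 20,000 simulated trials (ρ=0.5, 40 per arm, true effect −0.5) both estimators averaged −0.499. Their empirical SEs were 0.224 and 0.194, a variance ratio of 0.755 against 0.75 in theory.

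**Dropping only the treatment main effect.** Under the SAP's random-intercept-only covariance, the common-baseline constraint gives ratios of 0.847, 0.906, 0.964, 1.022 at k=0.8 and 0.921, 0.981, 1.041, 1.097 at k=0.7 (same ρ values). It can therefore be worse than the planned model.

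**The case against.** The planned model is standard and valid, and neither document contradicts itself on this point. The SAP text alone does not show that baseline is an outcome, and the Protocol's open reference to model building does not exclude a baseline term.

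The favourable row may also flatter the gain for MADRS. Entry requires a PHQ-9 of 10 or more (Inclusion and Exclusion Criteria), which plausibly narrows baseline spread. With k=0.8 and 20% missing by week 12, and the small-sample factor applied, the CI narrows by about 6%, 4%, 2% and 0.4% at N=80. At N=30 it narrows by 5%, 3% and 1%, then widens by about 1%. The argument applies less to WHOQOL, and N=30 is a low bound because the mixed models use all available data.

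The remedies also have costs. An unstructured four-visit covariance has 4 × 5/2 = 10 parameters, against 2 in the SAP model. A post-baseline model drops participants with no follow-up. The SAP is in the past tense, so the models appear to have been run.

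All of this stands as a limit on size and emphasis. It does not remove the point: the SAP names no baseline term, and adjustment gains or breaks even in every tabulated case before the small-sample factor. The possible loss is small.

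**Conclusion.** The concern holds as a matter of efficiency, with no error of validity. It is documented for the Protocol and inferred for the SAP. Over ρ 0.3–0.7 and k 0.7–1.0, with complete data and before the small-sample factor, adjustment cuts the variance of the between-arm contrast by 0–35% with categorical time and about 1–46% with linear time. The gain is largest when baseline and follow-up spreads are alike and correlation is modest. It nearly vanishes when baseline spread is narrow and correlation is high. The size rests on an SD ratio, a correlation and a time coding that neither document supplies, so confidence is medium. The change is worth making because it costs little and interval width is central to this study's purpose. That the comparison is unbiased presumes randomisation, a correct time shape and data missing at random.

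**What to change.** State in the SAP the visits modelled, the coding of time and the handling of baseline, and add one of these models:

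- **(a)** Weeks 6, 9 and 12 as outcomes, with baseline score and baseline-by-time as covariates, keeping age, gender and agency.
- **(b)** All four visits, with a common baseline mean and an unstructured covariance. Do not impose the common mean under the random-intercept-only covariance.

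Report the between-arm difference with its 95% CI at one end-of-treatment visit named in the SAP, beside the planned model. The visit needs naming because the Protocol's last primary visit is week 12, while the SAP defines remission and response at week 9. If the planned model has already been run, label the adjusted analysis as added afterwards and do not let it replace the planned result.

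The cost is one model and a few lines of text, with no new data and no change in conduct. Option (a) loses participants with no follow-up score. Option (b) keeps them but has more covariance parameters to estimate in a small sample.

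### The SAP omits the protocol's random slope without giving a reason; if true slopes vary, time is linear and at least three visits are used, the treatment-by-time standard error is too small

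*SAP*

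**What the plan says.** The protocol (STUDY DESIGN, Effectiveness objective) plans linear mixed models "with a subject-specific random intercept and slope and fixed effects for time, treatment, EM agency, LCSW, treatment x time interaction". They apply to the "primary (MADRS, WHOQOL assessed at baseline, 6, 9 and 12 weeks" measures, so four visits are planned for each primary outcome. It then adds "We will use model building and fitting strategies" and goes on to speak of a final model. It gives no rule for removing a term. It describes the focus of the analysis as being to "obtain preliminary signals of effectiveness by estimating effect sizes (95% CI" and to judge clinical relevance.

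The SAP uses two mixed models "to compare the trajectories of change in MADRS scores and WHOQOL scores" between arms. Their terms are treatment, "time, and their interaction, as well as a participant-specific random intercept", with adjustment for age and gender. On missing data it says: "Intent-to-treat analyses are presented with all available data in the mixed-effects models". It explains one model reduction: site and its interaction with treatment "were dropped as their effects were statistically non-significant". It says nothing about the slope: not whether it was fitted, what variance was estimated, or whether the fit converged. It also does not say which visits entered the models or whether time was linear or categorical. The only time points it names are baseline and Week 9, for remission and response.

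**The concern.** A random-intercept model lets patients differ in level but assumes that everyone in an arm has the same true rate of change. The models exist to compare trajectories between arms, so this assumption bears directly on the contrast of interest. If rates of change do differ, the uncertainty of the difference in mean slope includes the between-patient slope variance. The random-intercept model moves most of that variance into the residual, where it is averaged down over visits.

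Treatment by time is the between-arm contrast for both primary outcomes. The protocol calls the study inadequately powered and wants effect sizes with intervals to position a fully powered successor. Interval width is therefore one of the main products of the trial, and an interval that is too narrow would overstate the signal carried forward.

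**Working it through.** The documents give no variances, effect size or model N, so there is no figure of the plan to reproduce. What can be checked is the direction of the error and its size over a range.

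**Inputs from the documents.** Planned visits at weeks 0, 6, 9 and 12 (protocol); Week 9 as the endpoint for response and remission (SAP); two-sided 0.05 (SAP).

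**Assumed inputs.** Residual SD s = 5; slope SD t = 0.2, 0.4 or 0.6 points per week. The top value means an SD of 0.6 × 12 = 7.2 points in true 12-week change. These are MADRS-scale values.

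**Linear time, complete data.** Let n be the number of visits and Sxx the sum of squared deviations of the visit weeks from their mean.
- Weeks 0/6/9/12 (mean 6.75): Sxx = 45.5625 + 0.5625 + 5.0625 + 27.5625 = 78.75.
- Weeks 0/6/9 (mean 5): Sxx = 25 + 1 + 16 = 42.
- Weeks 0/9 (mean 4.5): Sxx = 20.25 + 20.25 = 40.5.

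Up to a factor for arm sizes, which cancels:
- true variance of the slope contrast = s²/Sxx + t²
- variance reported by the random-intercept model = s²/Sxx + t²/(n − 1)
- ratio r = √(true/reported); actual type I error = 2[1 − Φ(1.96/r)]

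Example, four visits, t = 0.4: true = 25/78.75 + 0.16 = 0.4775; reported = 25/78.75 + 0.16/3 = 0.3708; r = 1.13; type I error 8.4%.

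| Visits (weeks) | True SE ÷ reported SE, t = 0.2/0.4/0.6 | Type I error |
|---|---|---|
| 0, 6, 9, 12 | 1.04/1.13/1.24 | 5.9/8.4/11.5% |
| 0, 6, 9 | 1.02/1.06/1.11 | 5.4/6.4/7.7% |
| 0, 9 | 1.00/1.00/1.00 | 5.0/5.0/5.0% |

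With n = 2 the two variances are identical. At t = 0.4, changing the residual SD from 4 to 7 moves the type I error from 10.0% to 6.9% (four visits) and from 7.0% to 5.7% (three visits).

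**Categorical time, weeks 0/6/9/12, complete data.** For week k against baseline, true variance = 2s² + t²k² and reported variance = 2[s² + t²Sxx/(n − 1)]. Type I error for t = 0.2/0.4/0.6:
- week 6: 4.9/4.5/4.0% (slightly conservative)
- week 9: 5.3/5.9/6.7%
- week 12: 5.8/8.0/10.7%

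**Incomplete data, linear time.** These figures use the large-sample sandwich variance of the random-intercept estimator, intercept SD 6 (assumed), and random dropout leaving 60% with every visit:
- four visits (20/10/10/60% with one, two, three or all visits): 6.0/8.7/12.1%
- three visits (20/20/60%): 5.4/6.5/8.1%
- two visits, weeks 0 and 9, 40% missing the second: 5.1/5.5/6.1%; with an intercept-slope correlation of −0.3, 4.9/5.0/5.4%

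**Simulation check.** Random-intercept REML fits with the same three- and four-visit dropout (3,000 replicates) gave, at N = 80, 5.4/8.4/11.0% (four visits) and 5.4/7.0/8.3% (three visits). At N = 30 they gave 6.6/8.3/12.6% and 5.8/7.0/9.1%. These sizes are only a bracket: 80 is the recruitment target, and the SAP's 30 is the number with complete data for remission and response.

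**The case against.** The best defence is that the protocol itself foresees model building that leads to a final model. The SAP shows that reduction took place for site, so a random-intercept final model could be the result of the same process. This stands in part. A reader might infer that the SAP breaches the protocol, and the documents do not support that reading. What they show is that no criterion for removing the slope, and no result, is given anywhere.

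The second defence is that the harm depends on facts that are not given: material slope variance, linear time and at least three visits. That is correct. A reader might infer that the trial's intervals are known to be too narrow, but the documents do not establish this. If the models stop at Week 9, the three-visit figures apply, and at slope SD 0.2 the excess is hard to see. A separate simulation with no slope variance gave 5.4 to 5.8% at three or four visits, from small-sample error alone. The SAP also mentions only a p-value; the 95% CI is the protocol's intention.

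A reader might also infer that a two-visit model is always safe. It is exact only with complete data, and the SAP uses all available data. The error with missing second visits is small, but not zero.

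Finally, a random-slope fit may often land on the boundary in a sample this small. That is a reason to report the fit, not to leave it unmentioned.

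**Conclusion.** The point holds in conditional form and should be fixed. The two documents specify different random effects for both primary outcomes, and the SAP, which explains the removal of site, does not explain the absence of the slope. If true slopes vary, time is linear and at least three visits are used, the treatment-by-time standard error is too small, and so are the p-value and the CI width derived from it. With categorical time, the intervals at weeks 9 and 12 are too narrow and the one at week 6 is slightly too wide.

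The size in this trial is unknown. Under the assumed SDs it runs from negligible (5.4%, three visits, slope SD 0.2) to more than double the nominal level (11.5%, four visits, slope SD 0.6). These figures are for the MADRS scale; no range was worked out for WHOQOL. Confidence is medium, because the mechanism is certain but the variances, visits and time coding are not known.

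**What to change.** Report the protocol's random-intercept-and-slope model as the main treatment-by-time analysis for both outcomes, or use an unstructured within-person covariance if time is categorical. State the visits included and the coding of time. Show the random-intercept model as a labelled sensitivity analysis.

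If the slope was tried and removed, was estimated at zero, or did not converge, state the criterion and the result. The random-intercept model may then stay as the main analysis, with the random-slope fit, where it can be estimated, shown beside it.

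The cost is two refits on existing data. In simulations with three or four complete visits and no true slope variation, the interval was on average about 2 to 4% wider at N = 80 and 5 to 8% wider at N = 30. The range covers correlated and uncorrelated random effects. With correlated random effects, boundary fits occurred in 53 to 57% of data sets without slope variation and in 5 to 32% at slope SD 0.4, so the fallback will sometimes be needed. With incomplete data the point estimate may also move: under random dropout, the SD of the difference between the two estimates was 1 to 15% of the random-slope standard error.
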